11.0 SAFETY ANALYSES

The safety analysis will be performed for the double-blind treatment period and the double-blind down-taper period (only for safety parameters collected during the double-blind down-taper period), separately, using the Safety Population unless stated otherwise.

The safety parameters will include adverse events (AEs) and clinical laboratory parameters, vital sign measurements, electrocardiographic (ECG) parameters, suicide risk assessment using the Columbia-Suicide Severity Rating Scale (C-SSRS), and growth evaluation. For each safety parameter, the last nonmissing safety assessment before the first dose of investigational product will be used as the baseline for all analyses of that safety parameter. Continuous variables will be summarized by number of patients and mean, SD, median, Q1, Q3, minimum, and maximum values. Categorical variables will be summarized by number and percentage of patients.

For patients who take the double-blind down-taper investigational product, the double-blind treatment period starts with the first dose of double-blind investigational product and ends with the last assessment date up to the first dose of the double-blind down-taper investigational product. The double-blind down-taper period starts one day after the end of the double-blind treatment period and ends with the latter of the last dose of the double-blind down-taper investigational product and the last assessment date.

For patients who do not take the double-blind down-taper investigational product, the double-blind treatment period starts with the first dose of double-blind investigational product and ends with the latter of the last dose of the double-blind investigational product and the last assessment date.

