9.4.5.3 Double-Blind Down-Taper Period

All randomized patients who complete the 8-week double-blind treatment period and patients who prematurely discontinue from the study before completing 8 weeks of double-blind treatment should enter the 1-week, double-blind down-taper period unless it is considered not clinically appropriate by the Investigator. The double-blind down-titration regimen is as follows:

- Levomilnacipran 40 mg/day and 80 mg/day: Days 1-2, 40 mg/day; Days 3-7, 20 mg/day
- Fluoxetine 20 mg/day: Days 1-7, 10 mg/day

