9.7.6 Safety Analyses

The safety analysis will be performed for the double-blind treatment period and double-blind down-taper period separately using the Safety Population. The safety parameters will include AEs, clinical laboratory parameters, vital sign measurements, ECG parameters, C-SSRS, and growth evaluations. For each safety parameter, the last assessment made before the first dose of double-blind investigational product will be used as the baseline for all analyses of that safety parameter.

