9.7.6.1 Adverse Events

An AE (classified by preferred term) that occurs during the double-blind treatment period or during the double-blind down-taper treatment period will be considered a treatment-emergent adverse event (TEAE) if it was not present before the date of the first dose of double-blind investigational product or was present before the date of the first dose of double-blind investigational product and increased in severity during the double-blind treatment period or during the double-blind down-taper period, respectively. If more than 1 AE is reported before the date of the first dose of double-blind investigational product and coded to the same preferred term, the AE with the greatest severity will be used as the benchmark for comparison with the AEs occurring during the double-blind treatment period or during the double-blind down-taper period that were also coded to that preferred term. An AE that occurs more than 30 days after the date of the last dose of double-blind investigational product will not be counted as a TEAE.

An AE occurring during the double-blind down-taper period will be considered a newly emergent AE if it was not present before the start of the double-blind down-taper period or was present before the start of the double-blind down-taper period but increased in severity during the double-blind down-taper period. The newly emergent AEs during the double-blind down-taper period will be summarized by body system, preferred term, and treatment group.

The number and percentage of patients reporting TEAEs in each treatment group will be tabulated by system organ class and preferred term; by system organ class, preferred term, and severity; and by system organ class, preferred term, and causal relationship to the investigational product. If more than 1 AE is coded to the same preferred term for the same patient, the patient will be counted only once for that preferred term using the most severe and most related occurrence for the summarization by severity and by causal relationship to the investigational product.

The distribution of TEAEs by severity and causal relationship to the investigational product will be summarized by treatment group.

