6.3 SAFETY POPULATION

The Safety Population will consist of all patients in the Randomized Population who received at least 1 dose of double-blind investigational product.

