11.3 VITAL SIGNS

Descriptive statistics for vital signs (sitting radial pulse rate, sitting systolic and diastolic blood pressure, body weight and height) and changes from baseline values at each visit, and at the end of double-blind treatment period, and at the end of double-blind downtaper period will be presented by treatment group. Only patients with available baseline and at least 1 postbaseline assessment will be included in the summary. Vital sign values will be considered PCS if they meet both the observed-value criteria and the change-from-baseline criteria listed in Table 11–2. The number and percentage of patients with PCS postbaseline values will be tabulated by treatment group separately for the double-blind treatment period and the double-blind down-taper period. The percentages will be calculated relative to the number of patients with available baseline and at least 1 postbaseline assessment. The numerator will be the total number of patients with available baseline values and at least 1 PCS postbaseline value. A supportive listing of patients with PCS postbaseline values will be provided, including the PID number, and baseline and all postbaseline (including non-PCS) values.

In addition, a listing of all AEs that occurred in patients who had PCS postbaseline vital sign values will be provided.

	Table 11–2.	Criteria for	Potentially	Clinically	Significant	Vital Signs
--	--------------------	--------------	-------------	------------	-------------	-------------

		Criteria ^a			
Parameter	Flag	Observed Value	Change From Baseline		
Sitting systolic blood	High	≥ 140	Increase of ≥ 20		
pressure, mm Hg	Low	≤ 80	Decrease of ≥ 20		
Sitting diastolic blood	High	≥ 100	Increase of ≥ 15		
pressure, mm Hg	Low	≤ 50	Decrease of ≥ 15		
0:44:	High	≥ 130	Increase of ≥ 15		
Sitting pulse rate, bpm	Low	≤ 45	Decrease of ≥ 15		
Waisht Isa	High	_	Increase of ≥ 7%		
Weight, kg	Low	_	Decrease of ≥ 7%		

a A postbaseline value is considered potentially clinically significant if it meets both the observed-value and the change-from-baseline criteria.

bpm = beats per minute.

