11.5.1 Columbia-Suicide Severity Rating Scale

For the C-SSRS, the number and percentage of patients with any suicidal ideation or suicidal behavior at Baseline (lifetime history), and during the double-blind treatment period and during double-blind down-taper period will be summarized by treatment group for the Safety population. The distribution of responses for the most severe suicidal ideation and the most severe suicidal behavior will also be summarized by treatment group, separately for the lifetime history, the double-blind treatment period, and the double-blind down-taper period. Supportive listings will be provided and will include the PID number, treatment group, visit number, lifetime history, and postbaseline values for each patient. Intensity of ideation, suicidal behavior type, and lethality of suicidal behavior will also be included in these listings. A listing of all AEs occurring in patients who have suicidal ideation or suicidal behavior will also be provided.

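### Down-taper AE and C-SSRS percentages use the full Safety Population, although patients who take no taper product have no down-taper period under the SAP's own definition

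*SAP*

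**What the plan says.** SAP 11.0 analyses safety in the treatment period and the "double-blind down-taper period (only for safety parameters collected during the double-blind down-taper period), separately, using the Safety Population unless stated otherwise". Protocol 9.7.6 has the same rule: the two periods are analysed with the "double-blind down-taper period separately using the Safety Population". SAP 6.3 admits to that population every randomized patient who "received at least 1 dose of double-blind investigational product"; a taper dose is not required. SAP 6.0 lists four populations, and none is limited to taper patients.

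SAP 11.0 then defines the periods in two paragraphs. The one for patients who take taper product has a treatment period followed by a taper period. The one for everyone else has only a treatment period, which runs to the later of the last dose and the last assessment.

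Not everyone is bound to taper. Protocol 9.4.5.3 says that completers and early discontinuers alike "should enter the 1-week, double-blind down-taper period unless it is considered not clinically appropriate by the Investigator".

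On the individual parameters:

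- C-SSRS (SAP 11.5.1): ideation and behavior "during the double-blind treatment period and during double-blind down-taper period will be summarized by treatment group for the Safety population".
- TEAEs (SAP 11.1): numbers and percentages are given for each period, with no denominator of their own, so the SAP 11.0 default applies.
- Vital-sign PCS values (SAP 11.3), also tabulated by period: "The percentages will be calculated relative to the number of patients with available baseline and at least 1 postbaseline assessment".
- Protocol 9.7.6.1 adds a table that SAP 11.1 does not contain: "The newly emergent AEs during the double-blind down-taper period will be summarized by body system, preferred term, and treatment group".

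SAP 7.0 counts taper entrants and taper completers by arm. SAP 18.0 records no changes from the protocol.

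**The concern.** A percentage for a period should be based on patients who could contribute an event in that period. Here the numerator is limited by definition to takers, while the denominator includes everyone dosed. The taper tables are the only tables that isolate the week of dose reduction. They cover suicidal ideation and behavior, a stated focus of the Data Monitoring Committee in Protocol 9.10. A diluted percentage makes that week look quieter than it was for the patients who went through it. If the arms differ in how many patients skip the taper, they are diluted by different amounts.

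The period rule has a second effect. A patient who stops without tapering still returns for Visit 9/SFU about a week later (Protocol 9.5.5.7). Because the treatment period of such a patient runs to the last assessment, AEs and C-SSRS findings from the week after an untapered stop are counted as treatment-period findings.

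**Working it through.** The plan states no figure for taper rates or taper entry, so there is nothing of its own to reproduce.

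**Inputs.** Planned arm size is 160 (SAP 14.0); I assume that all are dosed. The taker share e is not in the documents and is varied. The rate r among takers is set at 5% for illustration. The only attrition figure is the 17% dropout in SAP 14.0. It is not a non-entry rate, because early discontinuers are also expected to taper. It enters below only as the case in which every dropout skips the taper (e = 0.83).

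**Formula.** With x patients having an event in the taper period, reported rate = x / N(safety) = [x / N(takers)] × [N(takers) / N(safety)] = r × e. The relative understatement is 1 − e.

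| Assumed e | Takers of 160 | Reported when r = 5% | Relative understatement |
|---|---|---|---|
| 1.00 | 160 | 5.00% | 0% |
| 0.95 | 152 | 4.75% | 5% |
| 0.90 | 144 | 4.50% | 10% |
| 0.83 | 132.8 | 4.15% | 17% |
| 0.75 | 120 | 3.75% | 25% |
| 0.60 | 96 | 3.00% | 40% |

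In counts: 8 patients with an event are 8/160 = 5.0% of the arm, but 8/132.8 = 6.0% of takers at e = 0.83.

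**Between arms.** With the same r in both arms, the apparent ratio is e(levomilnacipran) / e(placebo).

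- 0.83 against 0.83: 4.15% in each arm, ratio 1.00.
- 0.85 against 0.95: 4.25% and 4.75%, ratio 0.89. A true excess of 0.95/0.85 = 1.12-fold in the lower-entry arm would show as no difference.
- 0.75 against 0.95: 3.75% and 4.75%, ratio 0.79. The excess hidden is 0.95/0.75 = 1.27-fold.

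These splits are assumed; the documents give no entry rate for any arm.

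**Vital-sign PCS.** Read literally, the SAP 11.3 denominator is met by any reading from Week 1 to Week 8, so it admits non-takers to the taper table. Since the sentence follows an instruction to tabulate each period separately, it can also be read as requiring a reading inside the period. The text does not settle which.

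**Newly emergent AEs.** Protocol 9.7.6.1 judges these against status before the taper. SAP 11.1 sets its benchmark before the first double-blind dose and has no newly emergent category, while SAP 18.0 reports no change.

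**The case against.** **The denominator is partly inferred.** SAP 4.0 places table specifications in a separate document that was not supplied, and those shells may head the taper columns with the number entering the taper. That possibility stands. But SAP 11.5.1 names the Safety Population explicitly for the taper C-SSRS summary, and the SAP text should govern the shells.

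**The size is unknown.** A reader might infer that taper rates will be 17% too low, or that levomilnacipran will be favored because more of its patients skip the taper. The documents support neither: they give no non-entry rate, and nothing in them shows that skipping differs by arm.

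**Data are not lost.** A reader might take the taper tables as the only withdrawal data in the trial. They are not. Non-takers have AEs and C-SSRS recorded at Visit 9/SFU, TEAEs run to 30 days after the last dose, and C-SSRS listings are by patient and visit. What is missing is a summary that separates these data from on-treatment findings.

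**A reader can rescale.** Event counts are unaffected, SAP 7.0 gives entry by arm, and the protocol synopsis calls safety analyses descriptive. This is fair and limits the harm, but it leaves every reader to correct the tables.

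**The SAP follows the protocol here.** Protocol 9.7.6 names the same population, so the denominator is not an SAP departure. Both documents share the gap, and changing it must be recorded as a change.

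**A takers-only comparison is not randomized.** Taper entry is an investigator decision after randomization, so the new denominator removes dilution but not selection. This stands and shapes the fix.

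**Little AE content may be missing.** SAP 11.1 opens a new record with a new onset date whenever an AE worsens. If AEs are assigned to periods by onset date, the taper TEAE table captures most of what the protocol calls newly emergent. What remains certain is the unlisted omission of a protocol table.

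**Conclusion.** The point holds as a defect in the rule as written. For taper TEAEs and C-SSRS, the SAP pairs a numerator that only takers can enter with a denominator of all dosed patients, so the reported percentage is the takers' rate times the taker share. The consequence is conditional: no understatement if every patient tapers, 5% to 40% relative over an assumed share of 0.95 to 0.60, and a distorted between-arm ratio only if entry differs by arm. It rests on the SAP text being applied literally. For vital-sign PCS values the finding is ambiguity, not error. The newly emergent AE table is a real but secondary mismatch. Primary efficacy and power are not affected. The change should be made because it is cheap and concerns suicidality reporting, not because bias has been shown.

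**What to change.** 1. In SAP 6.0 and 11.0, define a Down-taper Safety Population: Safety Population patients with at least one dose of down-taper product.
2. Use it as the denominator for taper-period AE, C-SSRS and vital-sign PCS tables (SAP 11.1, 11.3, 11.5.1). For C-SSRS and vital signs, also require at least one assessment inside the taper period, which resolves the wording in SAP 11.3.
3. Print taper entry by arm, already produced under SAP 7.0, beside these tables, and state that they compare a subset formed after randomization.
4. Summarize separately, by arm, the post-treatment AE and C-SSRS data, including Visit 9/SFU, of patients who took no taper product.
5. Record the change from Protocol 9.7.6 in SAP 18.0.
6. Either restore the newly emergent AE table of Protocol 9.7.6.1 in SAP 11.1, or list its removal in SAP 18.0.

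The cost is SAP wording, revised table headers, one added summary for non-takers, and either the restored AE table or a line in SAP 18.0. No new data are needed. Where some patients skip the taper, any nonzero taper AE percentage rises; where all taper, it is unchanged.

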9.5.5.6 Visit 8 (End of Week 8 or Early Termination Visit)

All randomized patients should be seen for a final assessment at Visit 8/ET. A *final assessment* will be defined as completion of the evaluations scheduled at the end of Week 8 or ET Visit. The following procedures will be performed at Visit 8:

- Review and record AEs
- Review concomitant medications
- Measure vital signs (including height, measured by stadiometer)
- Perform ECG
- Complete physical examination

- Collect blood and urine samples for clinical laboratory determinations
- Serum β -hCG pregnancy test (females of childbearing potential only)
- Complete efficacy evaluations
 - Administer CDRS-R (caregiver and patient)
 - Administer CGI-S
 - Administer CGI-I
- Administer C-SSRS (Since-Last-Visit). Results should be evaluated by the Investigator or designee before the patient leaves the study center
- Confirm investigational product return and assess investigational product compliance
- If entering down-taper period: dispense double-blind down-taper investigational product for the next visit per IWRS assignment and provide written and verbal instructions for dosing to patient and caregiver. Document that instructions were given in source documents
- If Visit 8 is done remotely, the study drug may be sent to patients via preferred courier or via curbside pickup must be approved in advance by the Sponsor. All attempts must be made to collect safety labs
- Schedule Visit 9/SFU: 1 week (\pm 3 days) after Visit 8

Any clinical findings observed during this visit, including clinically significant laboratory abnormalities observed at prior visits, will be followed until the condition returns to prestudy status, has resolved or stabilized, or can be explained as being unrelated to the investigational product.

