9.5.5.7 Visit 9 (End of Week 9/Safety Follow-up Visit)

All randomized patients must complete Visit 8/ET Visit and, at the end of the double-blind down-taper period, return for Visit 9/SFU Visit. Patients who do not enter the double-blind down-taper period must return for Visit 9/SFU Visit approximately 1 week after Visit 8/ET.

The following procedures will be performed at Visit 9:

- Review and record AEs
- Review concomitant medications

- Measure vital signs
- Administer C-SSRS (Since-Last-Visit). Results should be evaluated by the Investigator or designee before the patient leaves the study center
- Confirm investigational product return and assess investigational product compliance (for patients who enter the double-blind down-taper period)

Any clinical findings observed during this visit, including clinically significant laboratory abnormalities observed at prior visits, will be followed until the condition returns to pre-study status, has resolved or stabilized, or can be explained as being unrelated to the investigational product. If a follow-up visit is necessary, it should take place within 30 days of investigational product termination.

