Vital signs (BP, pulse, weight)		X	X	X	X	X	X		X
Vital signs (BP, pulse, weight and height ^g)	Xe							X	
K-SADS-PL ^h	X								
CDRS-R	X	X	X	X	X	X	X	X	
CGI-S	X	X	X	X	X	X	X	X	
CGI-I			X	X	X	X	X	X	
C-SSRS	X	X	X	X	X	X	X	X	X
PK sampling ⁱ					X	X	X		
AEs	X	X	X	X	X	X	X	X	X
IP dispensing		X	X	X	X	X	X	X ^j	-
IP return			X	X	X	X	X	X	X ^j
IP compliance			X	X	X	X	X	X	\mathbf{X}^{j}

Note: If necessary, visits may be conducted up to 3 days before or after scheduled visits relative to the Baseline Visit (Visit 2).

a After assent and consent are obtained, the screening period may be up to 5 weeks in duration.

an PLC Page 9

- b Visit 8 assessments to be completed for all randomized patients who complete the study or discontinue before Week 8
- c All randomized patients must complete Visit 8/ET and, at the end of the down-taper period, return for Visit 9/SFU. Patients who do not enter the down-taper period must return for Visit 9/SFU approximately 1 week after Visit 8/ET Visit.
- d If the parent(s), guardian, or legally authorized representative (LAR) is also the patient's caregiver, he/she will be asked to sign both the parent and caregiver consents.
- e May be repeated at the Investigator's discretion before Visit 2.
- f A pregnancy test will be obtained for female patients of childbearing potential only.
- g Height will be recorded at Screening (Visit 1) and Visit 8/ET using a stadiometer.
- h K-SADS-PL data will be retained as source documents at the site.
- i *PK only collected on patients aged 7-11 years.* Sparse PK blood samples will be collected during Visit 5 (at predose and 1-4 hour postdose), Visit 6 (4-6 hours postdose), and Visit 7 (6-8 hours postdose). At Visit 5, or at any 24-hour period between Visit 5 and Visit 7, inclusive, serial blood samples will be collected from a subset of consented 7-11-year-old patients instead of sparse PK samples at the following time points: predose [20-24 hours after the most recent dose], and 2, 4, 6, 8, 10-12, and 24-hours postdose.
- For patients entering the double-blind down-taper period.

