16.1 VISIT TIME WINDOWS

Table 16–1 and Table 16–2 present the visits assigned for efficacy and safety analyses and the corresponding range of treatment days (window) during which an actual visit may occur.

Table 16–1. Visit Time Windows for Double-Blind Treatment Period

Derived Visit	Scheduled Visit Daya	Window
Baseline	Week 0 (Day 1)	Days ≤ 1
Week 1	End of Week 1 (Day 8)	Days [2, 11]
Week 2	End of Week 2 (Day 15)	Days [12, 18]
Week 3	End of Week 3 (Day 22)	Days [19, 25]
Week 4	End of Week 4 (Day 29)	Days [26, 35]
Week 6	End of Week 6 (Day 43)	Days [36, 49]
Week 8	End of Week 8 (Day 57)	Days ≥ 50 days and within double-blind treatment period
End of double-blind treatment period ^b	Final or Termination Visit	during the double-blind treatment period

a Relative to the date of the first dose of double-blind investigational product. Day 1 = the date of the first dose of double-blind investigational product. There is no Day 0 or Week 0.

Table 16–2. Visit Time Windows for the Double-Blind Down-Taper period

Derived Visit	Scheduled Visit	Window
Week 9	End of Week 9	Within the double-blind down-taper period (from 1 day after the end of double-blind treatment period to the end of the double-blind down-taper period)
End of double-blind down-taper period ^a	Final of termination visit during the double-blind down-taper period.	

a Presented in analysis tables for safety parameters collected during the double-blind-down-taper period. If any assessments are repeated at the end-of-double-blind-down-taper-period visit, the algorithm in Section 16.4 will be used to determine which values are used in the analysis.

b Presented in analysis tables for safety parameters, including but not limited to electrocardiograms, clinical laboratory values, and vital signs, and C-SSRS. If repeat assessments occur at the end of double-blind treatment period visit, the algorithm in Section 16.4 will be used to determine which values are used in the analysis.

If the visit date is on or after the date of the first dose of double-blind investigational product, the study day is calculated by visit date – date of the first dose of double-blind investigational product +1. If the visit date is before the date of the first dose of double-blind investigational product, the study day is calculated by visit date – date of the first dose of double-blind investigational product. Therefore, a negative day indicates a day before the start of the double-blind investigational product.

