If a patient has 2 or more visits within the same window, the last visit with a nonmissing value will be used for analysis.

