16.4 REPEATED OR UNSCHEDULED ASSESSMENTS OF SAFETY PARAMETERS

If a patient has repeated assessments before the date of first dose of double-blind treatment period the results from the final nonmissing assessment made before the date of the first dose of double-blind investigational product will be used as baseline. If end-of-double-blind-treatment period assessments are repeated or if unscheduled visits occur, the last nonmissing postbaseline assessment during the double-blind treatment period will be used as the end-of-double-blind-treatment-period assessment for generating summary statistics. Likewise, if end of double-blind down-taper period assessments are repeated or if unscheduled visits occur, the last non-missing assessment during the double-blind down-taper period will be used as the end-of-double-blind-down-taper-period assessment for generating summary statistics. However, all postbaseline assessments will be used to determine PCS values for laboratory parameters, vital signs and ECG parameters, and to determine most severe suicidal ideation and most severe suicidal behavior from C-SSRS. All assessments will be presented in the data listings.

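### SAP 11.0 sets no end to the treatment period of patients who take no down-taper product, so their post-treatment Visit 9 pulse, BP and weight fall into the Week 8 and other on-treatment rows

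*SAP*

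**What the plan says.** SAP 11.0 defines the double-blind treatment period by two adjacent rules. For patients who take down-taper product, the period closes at the last assessment up to the first taper dose. For patients who take none, it "ends with the latter of the last dose of the double-blind investigational product and the last assessment date". No definition or upper limit is given for that last assessment date.

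Patients who skip the taper are not finished at Visit 8/ET. Protocol 9.5.5.7 states: "Patients who do not enter the double-blind down-taper period must return for Visit 9/SFU Visit approximately 1 week after Visit 8/ET". Protocol 9.5.5.6 sets the timing, "Schedule Visit 9/SFU: 1 week" with a 3-day tolerance either way. Protocol 9.5.5.7 lists vital signs among the Visit 9 procedures, and in SAP Table 4-2 the row without height, "Vital signs (BP, pulse, weight", is marked at Visit 9/SFU.

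Four rules in SAP Section 16 decide where those values go:
- Week 8 (Table 16-1): "Days ≥ 50 days and within double-blind treatment period".
- Week 9 (Table 16-2): "Within the double-blind down-taper period (from 1 day after the end of double-blind treatment period" to the end of that period.
- Several visits in one window (16.1): "If a patient has 2 or more visits within the same window, the last visit with a nonmissing value will be used for analysis".
- End-of-treatment safety value (16.4): when assessments are repeated or unscheduled visits occur, "the last nonmissing postbaseline assessment during the double-blind treatment period will be used as the end-of-double-blind-treatment-period assessment".

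SAP 11.3 summarises vital signs at each visit and at the end of the treatment period. SAP 11.5.2 tests the change to Week 8 in age- and gender-adjusted height and weight. The protocol's growth test (9.7.6.5.2) covers height only.

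**The concern.** SAP 11.0 defines a down-taper period only for patients who take taper product. A no-taper patient's Visit 9 therefore cannot be Week 9. If it counts as that patient's last assessment, it lies inside the treatment period and must take a Table 16-1 label.

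The Week 8 vital-sign row, and the earlier rows for early terminators, would then mix values taken at Visit 8/ET with values taken about a week later, when treatment has normally ended. The mixing would be confined to one group, because the Visit 9 values of taper patients go to the down-taper period. That group is everyone who takes no taper product for whatever reason: investigator judgement, refusal, or product dispensed but not taken. It is likely to be a selected group, and its share may differ between arms.

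At stake are the by-visit pulse, BP and weight summaries, probably their end-of-treatment row, and one test that the SAP added (weight z-score).

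**Working it through.** The plan states no figure on this point to reproduce. The check applies the SAP's own windows to the visit days that the protocol allows.

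**Inputs**
- Table 16-1 windows, in study days: Week 1 = 2–11, Week 2 = 12–18, Week 3 = 19–25, Week 4 = 26–35, Week 6 = 36–49, Week 8 = 50 onward.
- Visit 8 is 8 weeks ± 3 days after Visit 2. If the first dose is taken the day after Visit 2, this is Day 53–59; if on the same day, Day 54–60. Together: Days 53–60.
- Visit 9 is 7 ± 3 days after Visit 8/ET, a gap g of 4 to 10 days.

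**Completers.** There are 8 Visit 8 days × 7 gaps = 56 combinations. Visit 9 falls between Day 53 + 4 = 57 and Day 60 + 10 = 70. In all 56 both visits are on Day 50 or later, so both are Week 8 and the later one is used. Example: Visit 8 on Day 57 and Visit 9 on Day 64 give a Week 8 value from Day 64.

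**Early terminators.** ET day x runs from 2 to 56 (55 days), and Visit 9 is on day x + g.

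| Gap g | Same window (ET value replaced) | Later window (extra on-treatment visit) | Visit 9 labelled Week 8 |
|---|---|---|---|
| 4 days | 35 | 20 | 11 (x = 46–56) |
| 7 days | 20 | 35 | 14 (x = 43–56) |
| 10 days | 11 | 44 | 17 (x = 40–56) |

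At g = 7 the replaced days are x = 2–4 (3 days), 26–28 (3), 36–42 (7) and 50–56 (7): 3 + 3 + 7 + 7 = 20, leaving 55 − 20 = 35. Examples: ET on Day 14 gives Visit 9 on Day 21, labelled Week 3; ET on Day 49 gives Visit 9 on Day 56, labelled Week 8. These are counts of days, not of patients.

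**Weight z-score.** The change to Week 8 uses the Week 8 weight. It therefore takes the Visit 9 weight for no-taper completers and for early terminators whose Visit 9 falls on Day 50 or later. Height is measured only at Visit 1 and Visit 8/ET, so the height test is untouched.

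**End-of-treatment row.** The window of this row in Table 16-1 is again the treatment period of SAP 11.0, which on the literal reading contains Visit 9. Section 16.4 then selects the last nonmissing value. This step is less firm than the Week 8 step, for the reasons given under the objection.

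**Not affected.** CDRS-R, CGI-S, CGI-I, scheduled labs, ECG and height are not collected at Visit 9.

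**The case against.** The strongest reply is that the sponsor meant Visit 8/ET. Several places point that way:
- Table 16-1 labels the end-of-treatment row as the final or termination visit.
- Protocol 9.5.5.6 ties the final assessment to the Week 8 or ET evaluations.
- Both schedules place Visit 9/SFU under the down-taper heading for everyone.
- SAP 17.2 refers to a follow-up period.

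This is good evidence of intent, but none of it defines or caps the last assessment date, and SAP 11.0 creates no follow-up period. A programmer following the text still has only Table 16-1 for these values.

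A second reply succeeds in part. A reader might infer that Visit 9 certainly becomes the end-of-treatment value for every no-taper patient. The documents do not go that far. Section 16.4 applies when end-of-period assessments are repeated or unscheduled visits occur, and footnote b of Table 16-1 also speaks of repeats. Visit 9 is a scheduled visit and not plainly a repeat of Visit 8. The end-of-treatment route is therefore a likely reading, not a certain one. The Week 8 route does not depend on 16.4.

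A reader might also infer that only patients judged unsuitable for the taper are affected. SAP 11.0 turns on not taking taper product, which is wider.

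Finally, an inclusive end date has a purpose: without it, Visit 9 safety data of no-taper patients would belong to no defined period. That stands for TEAEs, PCS values and C-SSRS findings, which are counted without overwriting anything. It does not justify replacing a Visit 8 measurement.

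**Conclusion.** The point holds as a minor specification gap. Followed as written, the rules put post-treatment pulse, BP and weight into the Week 8 row for every no-taper completer with nonmissing Visit 9 values. For no-taper early terminators they put such values into Week 8 or an earlier on-treatment row. The weight z-score test to Week 8 is affected in the same way, and the end-of-treatment row probably is. This rests on reading the last assessment date to include Visit 9; the text permits that reading, though it was probably not intended.

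The size is not derivable. An arm's mean would move by p × d, where p is the share of that arm whose value comes from a no-taper Visit 9 and d is their mean Visit 9 minus Visit 8/ET difference. A reader might take p from the 17% dropout rate in SAP 14.0, assume d = 10 bpm for pulse, and obtain 0.17 × 10 = 1.7 bpm. The documents do not support that figure. The 17% is a sample-size assumption about dropout, early terminators should by default enter the taper, some will not return for Visit 9, and d appears nowhere.

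The harm is confined to descriptive vital-sign rows and one SAP-added test. No efficacy conclusion depends on it.

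**What to change.** Add to SAP 11.0 and 16.1 that, for patients who take no down-taper product, Visit 9/SFU vital signs and weight are not assigned to any Table 16-1 window or to the end-of-treatment row, and are summarised in a separate post-treatment follow-up row. The treatment-period definition can otherwise stay, so TEAE, PCS and C-SSRS counting need not change and no second end date is needed.

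The cost is one sentence of SAP text, a small change to the derivation code, and one extra row in the vital-sign tables. No new data are needed. One limit remains: an ET visit held some days after the last dose still counts as treatment period, so the mixing is reduced but not removed.
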